A feasibility clinical trial conducted by our group tested the ReCognitionVR cognitive interventions on older and young healthy volunteers (Appendix A. Final Study Report). The results of this study showed that ReCognitionVR-based cognitive exercises were feasible, acceptable, and tolerable by older healthy subjects. In stage 2 of our research study, we want to evaluate the safety, feasibility, acceptability, and tolerability of VR-based cognitive exercises in 60-year-old or older patients following abdominal surgery admitted to the surgical floor at Houston Methodist Hospital (HMH). Our premise is that VR-based cognitive stimulation software will allow the controlled delivery of structured cognitive exercises focusing on orientation, attention, memory, and executive functions. The system will allow customized frequency and duration of cognitive exercises based on the users' difficulty level in a delightfully relaxed-environment with beach wave sounds.

Hypothesis:

We will test the hypothesis that the test population will find ReCognitionVR-based cognitive exercise safe, feasible, acceptable, and tolerable.

2. Purpose of the Study / Objectives

This study aims to assess the feasibility, acceptability, and safety of using ReCognitionVR-based software in older surgical patients. Results from this study will be used to inform the design of a future study in critically ill hospitalized patients at risk for delirium.

The question that drives this study is:

In surgical floor patients, what is the safety and feasibility of using the ReCognition VR-based cognitive exercise, and what is the acceptability and tolerability of the exercise?

OBJECTIVES AND ENDPOINTS

OBJECTIVES	ENDPOINTS	JUSTIFICATION FOR ENDPOINTS
Primary		
The primary objective of this study is the safety of VR-based cognitive stimulation exercises for older surgical patients.	The primary endpoint is the proportion of treatment-emergent adverse events (TEAE) in each group (experimental and control).	 To assess tolerability of ReCognitionVR-based cognitive stimulation exercises. Adverse events (e.g., cybersickness) will assess tolerability

Page 2 of 21

OBJECTIVES	ENDPOINTS	JUSTIFICATION FOR ENDPOINTS
		during engagement through exercise provided by ReCognitionVR games.
Secondary		

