 The secondary objectives are To assess the changes in vital signs during the exercise 	The secondary endpoints are: 1. Mean change from pre to 10 minutes: a. Pulse oximetry oxygen saturation (SpO2) b. Respiratory rate (RR)	Knowing the change in these biometric measures will assist in designing future investigations of patients at risk of
To assess change in vital signs at the end of the exercise	c. Blood pressure (BP) 2. Mean change from pre to end of VR session: a. SpO2 b. RR c. BP	delirium.
To assess the feasibility of VR-based cognitive stimulation exercises in older surgical patients.	using the ReCognitionVR-based cognitive exercise for 20 minutes by 70% of enrolled participants. using the ReCognitionVR-based cognitive exercise for 20 minutes by 70% of enrolled participants.	It is essential to know if participants can complete the exercise since an incomplete experience will prohibit the assessment of the other variables to be measured.
To determine the acceptability of VR-based cognitive stimulation exercises	the proportion of participants with a System Usability Scale (SUS) score >35.	Successful implementation depends on the acceptability of the intervention and is one of the main factors considered before adopting and implementing computerized cognitive software.

Page 3 of 21

OBJECTIVES	ENDPOINTS	JUSTIFICATION FOR ENDPOINTS
 To determine the accuracy of VR-games Technical difficulty with VR software 	 the proportion of participants who complete the game without any user errors. Number of attempts to complete the game. Number of software and device re-starts and re-sets. 	Accuracy is an essential variable in assessing the attention of the study subject. Attention is a prominent cognitive domain involved in delirium. Important to upgrade or incorporate advanced VR software.
Exploratory		
Exploratory outcome to report the episode of delirium	Confusion Assessment Method (CAM) tool (Appendix B) ⁶ or 4 A's Test score (Appendix C) ⁷ will be used to assess delirium.	Knowing the proportion of study subjects with new-onset delirium will assist in designing future investigations of patients at risk of delirium.

3. Background

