Data on interventions focused on early cognitive exercise using Virtual Reality Simulation, specifically using Oculus Quest 2 and Unity software, are limited. Moreover, many critical barriers to implementing cognitive training in clinical protocols exist. Cognitive stimulation through VR is a new and upcoming area in technology that is rapidly expanding but is currently limited in literature. A lack of understanding or appreciation for the evidence supporting cognitive stimulation through VR, specifically gamification, contributes to the barriers. The rapid increase and use of VR in other areas urges our team to seek this area for development.

Major goals: This proposal aims to assess the safety/tolerability, feasibility, and acceptability of VR-based cognitive interventions in older surgical patients using ReCognition VR software while providing easy delivery of cognitive stimulation exercises provided by VR.

Preliminary Study:⁵ Our group conducted a prospective, single center, randomized, controlled clinical trial in healthy volunteers from August 2021 to December 2022. Healthy volunteers were enrolled based on the American Society of Anesthesiologists (ASA) physical status classification system: ASA 1 included those aged >18 to 35 years, and ASA 2 included those aged >60 years. The study results (Appendix 1: Final Study Report) were as follows: Feasibility: All study participants in both ASA 1 and 2 groups completed the ReCognitionVR-based exercise with feasibility of 100%; Acceptability/Usability: The mean SUS scores for ASA 1 and ASA 2 were 88.17±12.83 and 88.67±9.90, respectively There were no statistically significant differences in SUS scores between ASA 1 and ASA 2 (p=0.81); Tolerability: Only four adverse events occurred during the study: 3 (20%) in the ASA1 group and 1 (6.67%) in the ASA2 group. Although 1/15 (6.67%) ASA 1 participants experienced transient dizziness and 1/15 (6.67%) ASA 2 participants had a vague undefined mind/brain fog, both participants completed the study interventions. One study participant, 1/15 (6.67%) from the ASA 1 group, experienced a transient increase in SBP >20% from baseline. No participant experienced more than one adverse event. No serious adverse events occurred. The procedure was not interrupted related to an adverse event.

4. Study Design

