The study is a single-center, prospective assessment of the feasibility, acceptability, and usability of ReCognition VR -based simulated cognitive stimulation to improve attention and focus in surgical patients.

Sample size: We will enroll 30 participants: 15 participants who are ≥60 years of age with traditional orientation methods and 15 participants who are ≥60 years of age and receive ReCognitionVR-based cognitive exercises.

Justification of sample size: The study is a feasibility study expecting that 70% of participants in the study intervention group will complete 20 minutes of the ReCognitionVR-based exercise, where each group will be evaluated separately. Descriptive statistics will be used to summarize the findings; 15 participants in each group will be recruited. The intent is that this study will provide information for a larger, subsequent clinical trial of patients ≥60 years old at risk for delirium.

Data and measures to be taken:

The endpoints for this feasibility study are:

Primary Objective:

Safety/Tolerability: We will examine measures that can inform on the safety of the experience to be used in the subsequent clinical trial. The measures are:

- 1. Mean change from pre to 10 minutes of the ReCognition VR-based exercise in:
 - a. SpO2
 - b. RR
 - c. Blood pressure (Mean BP, Systolic BP, and Diastolic BP)
- 2. Mean change from pre to end of the ReCognition VR-based exercise in:
 - a. SpO2
 - b. RR
 - c. Blood pressure (Mean BP, Systolic BP, and Diastolic BP)

Secondary Objectives:

Feasibility: 70% of participants in each group will complete 20 minutes of use of the ReCognition VR-based software (a binary outcome).

Acceptability: We will measure the acceptability and usability of the experience based on the proportion of participants with a SUS score >35.

VR-games Accuracy: We will report on the proportion of participants who complete the game without any user errors and the number of attempts each participant uses to complete the game.

Page 6 of 21

Exploratory Objective:

Delirium: We will assess delirium using CAM tool⁶ or the 4 A's test⁷. Delirium is defined as any positive CAM Score or/and score of 4 or above on the 4 A's test for 72 hours after study interventions.

Accessing data from medical records:

Medical records of the potential study subjects will be reviewed for medical history for the inclusion and exclusion criteria described below in section 10.

Data analysis plan:

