We will report the demographic variables of age, sex, race, and ethnicity for each group and the clinical characteristics and will review the patient's medical records for body mass index, history of hypertension with active management, drinking status, smoking status, ASA status, preexisting medical co-morbidities. If not found in the medical record, we will obtain this information.

[figure not shown]
The results of this study will be reported using descriptive statistics. Continuous variables will be reported as means with standard deviation or medians and interquartile range contingent on the normality of the distribution. Categorical variables will be reported using Chi-square or Fisher's exact test, as appropriate.

5. Study Intervention

- 1. Older patients (≥ 60 years old) scheduled to undergo abdominal surgeries (open or laparoscopic or robotic assisted), small bowel and large bowel surgery; cholecystectomy; Whipple procedure; pancreatectomy; splenectomy at HMH will be invited to participate.
- 2. We will screen patients for inclusion and exclusion criteria and will assign a screening number.
- 3. After signing informed consent, participants will be enrolled in the study and randomized using computer-generated randomization software to traditional orientation method (control) or ReCognitionVR-based cognitive exercises (experimental).
- 4. The experimental group will watch a video on using VR technology, placement of a VR headset, and assessment of baseline cognitive function using the Mini-Cog screening tool.
- 5. All participants will have a frailty screening assessment.9

Page 7 of 21

- 6. The Mini-Cog screening tool will assess the patient's cognitive status of all participants. (Appendix D)⁸
- 7. The experimental group will receive a 3D- ReCognitionVR-based simulated cognitive exercise program targeting attention, organizing thinking, and motor activities using VR games. The participant will receive study intervention after arrival to the room from the operating room, free of residual anesthesia, by measuring the Richmond Sedation Scale (RASS)- Appendix E^{10} score of 0.

- 8. The detail of the software as follows:
 - 3-D Recognition Virtual Reality-Based Simulation Sessions Program: Software Platform:

The VR platform will consist of

Page 8 of 21

- The VR headsets manufactured by the Oculus Quest 2 glasses (Facebook Inc., USA) with stereoscopic vision and stereo sound will be used to show the virtual world to participants.

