- Motion Sensor
- Flat Screen TV with Software

The VR headsets manufactured by the Oculus Quest 2 glasses (Facebook Inc., USA) with stereoscopic vision and stereo sound will be used to show the VR to study participants. After headset placement, the study participants will be able to follow instructions provided by virtual nurse AVATAR. The participants will receive low cognitive load exercises based on virtual reality techniques, including a relaxed environment, music therapy, time orientation, delivery instructions, and task completion motivation. The exercise task will focus on attention, organized thinking, and motor activities.

9. If you are in the traditional orientation method, you will be visited by a nurse at the start of each nursing shift. The nurse will ask you questions to check your memory and attention. Examples of questions include asking you for your name, the date, where you are, and what just happened to you. This will be repeated during every nurse shift change and is the usual care you would receive, even if you were not in the study. In this method, your vital signs (oxygen levels, how fast you are breathing, and your blood pressure) will be measured at different time points after your abdominal surgery as part of your standard care. When you wake up from surgery, you will have the traditional orientation questions asked of you until you are discharged from the hospital. Your participation in this study will be over after you leave the hospital.

Schedule of Activities

Procedures	Screening*	Day 1,	Day 1,	Day 1,	Day 1,	Post 24	Post 48	Post 72
		Time 1:	Time 2:	Time	Time	hours	hours	hours
		pre	10	3: post	4: end			
			minutes		of			
					study			
Visit number	Visit 0 or 1	Visit 1				Visit 2	Visit 3	Visit 4
Informed	X							
consent								
Demographics	X							
Medical history	X							
Randomization		X						
Administer			X-					
study								
intervention								
Concomitant	X							
medication								
review								

Page 9 of 21

Procedures	Screening*	Day 1, Time 1: pre	Day 1, Time 2: 10 minutes	Day 1, Time 3: post	Day 1, Time 4: end of study	Post 24 hours	Post 48 hours	Post 72 hours
Visit number	Visit 0 or 1	Visit 1				Visit 2	Visit 3	Visit 4
Physical exam (including height and weight)	X							
Frailty screening assessment	X							
Mini-Cog screening assessment	Х							
RASS Score	Х							
Pulse oximetry		X	Х	Х				
Respiratory rate		Х	Χ	Х				
Blood pressure		Х	Χ	Х				
System User Survey					Х			

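### Acceptability is summarised only as the share with SUS above 35, a cut-off that every pilot participant passed, and the plan does not settle who completes the SUS

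*Combined protocol and SAP*

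**What the plan says.** The hypothesis statement before Section 2 names acceptability as one of four properties: "We will test the hypothesis that the test population will find ReCognitionVR-based cognitive exercise safe, feasible, acceptable, and tolerable".

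The Section 2 table gives the objective as "To determine the acceptability of VR-based cognitive stimulation exercises" and the endpoint as "the proportion of participants with a System Usability Scale (SUS) score >35". Section 4 repeats that definition: "We will measure the acceptability and usability of the experience based on the proportion of participants with a SUS score >35". Neither place explains the choice of 35 or says what proportion would count as acceptable. Feasibility, by contrast, has a 70% target.

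Section 3 (Preliminary Study) reports from the healthy-volunteer pilot: "The mean SUS scores for ASA 1 and ASA 2 were 88.17±12.83 and 88.67±9.90, respectively". The group size of 15 appears in the adverse event fractions, for example "1/15 (6.67%) ASA 2 participants had a vague undefined mind/brain fog".

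The Section 4 data analysis plan has a general rule: "Continuous variables will be reported as means with standard deviation or medians and interquartile range contingent on the normality of the distribution". It does not mention the SUS.

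On who is surveyed:

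- Section 10 describes both arms of 15 and then gives the post-use usability and acceptability surveys to all participants.
- Section 5 (Dosing) says that those who receive about 20 minutes of VR complete the SUS. The Acceptability Survey paragraph that follows refers only to study participants.
- The System User Survey row of the Schedule of Activities names no arm.
- Controls receive nurse orientation and no VR: "If you are in the traditional orientation method, you will be visited by a nurse at the start of each nursing shift".

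**The concern.** Reducing a numeric score to pass or fail at a point far below the earlier results discards most of its information. The study is meant to inform a later trial in patients at risk of delirium. For that purpose a typical score near 60 differs materially from one near 90, yet both could give a proportion close to 100%.

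The survey wording raises a second problem. Staff who follow Section 10 literally would ask controls to rate a system that they never used. Their answers would not describe the VR software, and they could enter the denominator of the acceptability result.

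**Working it through.** **1. Did the cut-off separate anyone in the pilot?**

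Inputs (Section 3): mean 88.67, SD 9.90 (ASA 2); mean 88.17, SD 12.83 (ASA 1); n = 15 per group. For any set of n values, the lowest value compatible with a given mean and SD (n−1 divisor) is

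minimum = mean − SD × (n−1)/√n, with 14/√15 = 3.615.

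- ASA 2: 88.67 − 9.90 × 3.615 = 88.67 − 35.79 = 52.9
- ASA 1: 88.17 − 12.83 × 3.615 = 88.17 − 46.38 = 41.8

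If the SD used divisor n, the multiplier is √14 = 3.742 and the minima are 51.6 and 40.2. All four exceed 35. The bound needs no distributional assumption, so the endpoint would have read 15/15 in both groups.

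Reading ± as a standard error is not tenable on an assumed 0–100 scale. The implied SDs, 12.83 × √15 = 49.7 and 9.90 × √15 = 38.3, exceed the largest possible for those means (33.4 and 32.8).

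**2. How does the proportion respond if scores are lower here?**

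The documents do not say what surgical patients will score, so these are assumptions: a 0–100 scale; mean 60 or 50; SD 9.90 or 12.83 (pilot), 20 or 25 (assumed, because pilot SDs may be compressed near the top of the scale). The normal model is P(SUS > 35) = 1 − Φ((35 − mean)/SD). It would put 13% to 18% of scores above 100 at the pilot values, so a beta model on 0–100 with the same mean and SD is shown as well.

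| Mean | Model | SD 9.90 | SD 12.83 | SD 20 | SD 25 |
|---|---|---|---|---|---|
| 60 | Normal | 99.4% | 97.4% | 89.4% | 84.1% |
| 60 | Beta | 99.3% | 97.0% | 87.4% | 80.7% |
| 50 | Normal | 93.5% | 87.9% | 77.3% | 72.6% |
| 50 | Beta | 93.4% | 87.2% | 74.9% | 68.8% |

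Against the pilot's 100%, a mean of 60 lowers the expected proportion by about 1 to 19 points. A mean of 50 lowers it by about 6 to 31 points.

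**3. Precision with 15 patients**

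If all 15 pass, the exact 95% CI for the proportion is 78% to 100%. That interval contains every mean-60 value in the table and, at the two pilot SDs, every mean-50 value. The 95% CI half-width for mean SUS is 2.145 × SD/√15, which gives 5.5, 7.1, 11.1 and 13.8 points for the four SDs. Even the widest is well under the 29-point gap between the pilot mean and 60.

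**4. The denominator**

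As an illustration, suppose all 15 VR users score above 35. With VR users as the denominator the result is 15/15 = 100% (95% CI 78% to 100%). With all 30 participants, and controls having no qualifying score, it is 15/30 = 50% (95% CI 31% to 69%).

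**The case against.** - **Different population.** The pilot enrolled healthy volunteers. A reader might infer that 35 cannot discriminate in this trial. The documents do not support that: the bound concerns the pilot only, and the table shows the proportion moving noticeably at mean 50 or with a wide SD.
- **No planned comparison.** Sections 4 and 2 plan a description of acceptability, not a test against the pilot. A reader might infer that the endpoint fails such a test, but none is planned. The pilot serves here only to show how coarse the measure is.
- **A threshold is legitimate.** A mean can hide an unhappy minority: 13 patients at 90 and 2 at 25 average 81.3, while 13/15 (87%) pass. This stands, and it is why the proportion should be kept beside the mean.
- **Already covered.** The general rule for continuous variables, and the pilot's own use of mean and SD, may well lead to mean SUS being reported. That is likely, but the named endpoint does not commit to it.
- **A reason for 35 may exist.** It could lie in the SUS appendix or the pilot report, which are not in the supplied text. The point is limited accordingly.
- **The intended respondents are fairly clear.** A reader might infer that the plan requires controls to rate VR. The Section 2 objective, the post-use wording and the Dosing paragraph all point to VR users. What remains is the literal wording of Section 10 and an unstated denominator.
- **No success criterion.** A mean with a CI does not decide whether the exercise is acceptable. This stands: the change improves the description and does not supply a criterion.

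**Conclusion.** The point holds in a limited form. Acceptability is defined only by a cut-off that all pilot participants passed, given that ± is the SD and that all 15 per group gave a score. With 15 patients the proportion alone describes usability coarsely. Under the assumed means and SDs, a mean of 60 would still give an expected 81% to 99% above 35, and a mean of 50 about 69% to 94%. The lower ends of those ranges rest on assumed SDs of 20 to 25 that the documents do not give, so it would be wrong to call the endpoint insensitive in every plausible case. Who completes the SUS needs clarifying, although the intended reading is probably VR users. This is a modest reporting and wording point on a secondary endpoint of a descriptive study.

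**What to change.** - **Section 2 table and Section 4 (Acceptability):** report SUS in the VR arm as a mean, or a median under the data analysis plan's own rule, with a 95% CI. Include patients who stop the session early; Section 12 already retains and analyses data from participants who discontinue. Report the proportion above 35 alongside it, state the reason for 35, and name VR-arm participants as the denominator.
- **Section 10:** limit the sentence on post-use surveys to participants in the VR group.
- **Section 5:** make the Acceptability Survey paragraph and the System User Survey row of the Schedule of Activities match.

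The cost is protocol wording. No new data are needed, and up to 15 surveys are saved if controls would otherwise have been asked. The downside is that the acceptability result may look less favourable than a proportion near 100%.

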Number of software and device re-starts, re-sets.		Х	X					
Number of User errors			Х	Х	Х			
Number of game attempts			X	Х	Х			
Adverse event review and evaluation		Х	Х	Х	Х	Х	X	X
Pain scores (Numeric Pain Scale)	Х	Х	Х	Х	Х	Х	Х	X
Positive CAM or/and 4 A's Test	Х	Х				Х	Х	Х
Complete Case Report Forms (CRFs)	Х	Х			X			

^{*}Screening Visit and Day 1 may occur on the same day

Dosing:

The study participants will receive approximately 20 minutes of VR- based cognitive stimulation sessions and complete a post-user survey System Usability Scale.

Acceptability Survey:

Principal Investigator (PI) or a research team member will use the SUS survey to interview the study participants. (Appendix - F)

6. Drugs, Biologics, Devices

Specifically, VR will be simulated using UNITY software and Oculus Quest (two headsets) for this project. The use of ReCognitionVR software is investigational in this proposal. However, in Phase 1a study we evaluated the feasibility, safety, and acceptability of ReCognitionVR software in healthy elderly subjects. The result of the study is uploaded as a clinical study report in MORTI. Moreover, the use of VR software has been approved by FDA. There are multiple VR softwares that are approved by the FDA. Please see the link below for reference:

Augmented Reality and Virtual Reality in Medical Devices | FDA

7. Collaborative / Multi-site Research

N/A

8. Data Privacy / Confidentiality

Houston Methodist policies for Protected Health Information (PHI) will be followed, including all physical and electronic data security requirements, encrypted devices, and HM password-protected servers.

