- Pain scores (using numeric pain rating scale tool)
- Safety adverse events

Identifier (or parts of)	Recorded	Disclosed	Comment
All elements of dates (except year) for dates	Yes	No	Necessary for complete data
directly related to an individual, including			analysis
patient names, birth date, admission date,			
discharge date, and date of death; and all			
ages over 89 and elements of dates			
(including year) indicative of such age			
Phone numbers; Fax numbers	Yes	No	Necessary to complete a
			questionnaire
Medical record numbers	Yes	No	Necessary to organize data
			collection

Page 12 of 21

Identifier (or parts of)	Recorded	Disclosed	Comment
Any other unique identifying number,	Yes	No	Virtual cognitive
characteristic, or code			interventions are frequently
			delivered

9. Data and Specimen Banking

No specimens will be obtained, stored, or banked in this study.

10. Study Population

This study will be a single-center study of older patients who underwent abdominal surgeries and will be conducted at Houston Methodist Hospital. We will enroll 30 patients scheduled to undergo abdominal surgery who are ≥60 years of age. The rationale for enrolling older patients is that older surgical patients are at high risk for the development of delirium.

A total of 30 patients will be prospectively enrolled. 15 patients will receive the standard of care / re-orientation technique, and 15 patients will receive ReCognitionVR-based cognitive exercises. All participants will be given post-use surveys to assess usability and acceptability outcomes.

Inclusion Criteria:

- 1. Patients ≥ 60 are scheduled to undergo the following abdominal surgeries (open or laparoscopic or robotic assisted) small bowel and large bowel surgery; cholecystectomy; Whipple procedure; pancreatectomy; splenectomy.
- 2. RASS Score 0

Exclusion Criteria:

- 1. Subjects with baseline cognitive impairment.
- 2. Person with active psychiatric disorders and being treated with medications, especially schizophrenia.
- 3. Person who is deaf or blind.
- 4. Person with an underlying cognitive disorder or associated phobias (e.g., claustrophobia).
- 5. Person participating in other clinical trials involving drugs, biologics, devices, or behavioral interventions.
- 6. Active seizure disorders.

11. Screening and Recruitment

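### The delirium definition does not require a negative result before the session, so delirium already present can be counted in an endpoint meant to measure new-onset cases

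*Combined protocol and SAP*

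**What the plan says.** Four places in the combined protocol and SAP bear on this point.

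- **Section 4, Exploratory Objective**, gives the operative definition: "Delirium is defined as any positive CAM Score or/and score of 4 or above on the 4 A's test for 72 hours after study interventions". The opening words, "Delirium is defined as any positive CAM Score", carry no condition on earlier results, and neither does the rest of the sentence.
- **Section 2, objectives table, Exploratory row**, says only that CAM or 4AT "will be used to assess delirium". The justification beside it names the quantity wanted: "Knowing the proportion of study subjects with new-onset delirium will assist in designing future investigations of patients at risk of delirium".
- **Section 5, Schedule of Activities**, has a row labelled "Positive CAM or/and 4 A's Test" with five marks: Screening, Day 1 Time 1 (pre), and 24, 48 and 72 hours. Under Section 5, item 7, the session takes place after the participant returns from the operating room, so Time 1 reads as a post-operative assessment just before the session.
- **Section 10, Exclusion Criteria**, comes closest with "Subjects with baseline cognitive impairment" and "Person with an underlying cognitive disorder or associated phobias (e.g., claustrophobia". Neither names delirium or a positive CAM/4AT. Inclusion also requires a RASS of 0.

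The plan does not say how the Screening and Time 1 results are to be used, whether for eligibility, for the denominator or in the analysis.

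**The concern.** Any positive result in a window after the session is one quantity. New onset among people free of delirium at its start is another. The plan justifies the endpoint by the second and defines it by the first. The two differ when a participant is already positive before the session and remains so at a later assessment.

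That situation is plausible here. Participants are aged 60 or over and have just had abdominal surgery, and Section 10 itself calls older surgical patients a high-risk group for delirium. Delirium can arise between Screening and the session. The exploratory result is meant to help design the next trial, so an incidence that includes cases present beforehand would overstate what that trial should expect after the session. Delirium on days 1 to 3 is also part of the periodic safety review in Section 17, where a case that began earlier could be listed among events following the exercise.

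**Working it through.** The plan states no delirium rate and derives no sample size from one, so there is no figure to reproduce. The check is on the wording, followed by arithmetic for scale.

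**Inputs from the documents:** 15 participants per arm, 30 in all (Section 4, Sample size); CAM/4AT at Screening, Time 1, 24, 48 and 72 hours (Schedule of Activities).

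**Step 1. Apply each rule to the possible result patterns.**

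| Screening | Time 1 | 24 to 72 h | Section 4 rule | New since the session | New since Screening |
|---|---|---|---|---|---|
| negative | negative | positive | event | yes | yes |
| negative | positive | positive | event | no | yes |
| positive | positive | positive | event | no | no |
| negative | positive | negative | no event | no | yes |

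The Section 4 rule matches neither reading of new onset in every row. Against onset since the session it overcounts in rows 2 and 3. Against onset since Screening it overcounts in row 3 and misses row 4.

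**Step 2. Weight of a case.** One persisting pre-session case adds 1/15 = 6.7 percentage points to its arm; two add 2/15 = 13.3 points.

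**Step 3. Illustration.** Assume 2 true new-onset cases in an arm of 15, plus k participants positive before the session who stay positive. The written rule gives (2 + k)/15. New onset among those at risk gives 2/(15 − k).

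| k | As written | New onset among those at risk |
|---|---|---|
| 0 | 2/15 = 13.3% | 2/15 = 13.3% |
| 1 | 3/15 = 20.0% | 2/14 = 14.3% |
| 2 | 4/15 = 26.7% | 2/13 = 15.4% |
| 3 | 5/15 = 33.3% | 2/12 = 16.7% |

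**Step 4. Could such a participant turn up at all?** The documents give no pre-session prevalence p, so these values are assumed. The chance of at least one positive among n participants is 1 − (1 − p)^n.

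| Assumed p | One arm (n = 15) | Both arms (n = 30) |
|---|---|---|
| 2% | 26.1% | 45.5% |
| 5% | 53.7% | 78.5% |
| 10% | 79.4% | 95.8% |
| 20% | 96.5% | 99.9% |

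These are upper limits for miscounting at each p, because only cases still positive at 24 hours or later enter the outcome.

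**Step 5. Could a chance imbalance pass for an effect?** Take two such cases in one arm, none in the other, and no other events. The two-sided Fisher p-value is 2 × C(15,2)/C(30,2) = 2 × 105/435 = 0.48.

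**The case against.** **The passages can be read together.** Section 4 may define only what makes an assessment positive and over which window, leaving Section 2 to name the quantity and the schedule to supply the data. It is true that no data are lost and new onset can be tabulated from what is planned. But Section 4 is worded as the definition of the outcome, and no other text supplies the derivation. An analyst following it literally would count rows 2 and 3 of the first table.

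**New onset need not mean after the session.** The documents do not fix the reference point, and delirium arising between Screening and Time 1 is new in one sense. This stands, and it is why the reference must be written down. It does not rescue the current rule, which fails on that reading too.

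**Existing safeguards.** The cognitive exclusions and RASS 0 may keep some prevalent cases out, particularly at Screening. However, RASS measures sedation and agitation, and no rule ties a positive CAM/4AT to eligibility. Delirium arising after Screening is not addressed.

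**Generic magnitude.** The 6.7 points is the weight of any one participant on any binary outcome in this trial. That is correct: it shows the scale of an error, not its likelihood.

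**Controls.** Time 1 and the 72-hour window are tied to a session that controls do not have, so a new-onset rule alone would not be computable in half the sample. This stands and is taken into the fix. Separately, Section 5, item 9 ends control participation at discharge, so classification of anyone discharged before 72 hours needs stating under either definition.

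**Conclusion.** The point holds as a mismatch between the endpoint's stated purpose and its operative definition. A participant positive before the session and still positive afterwards can be counted as an outcome, at 6.7 percentage points per case in an arm of 15. The number of such cases is unknown; the prevalences and case counts used above are assumptions.

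A reader might infer two stronger things that the documents do not support. The first is that pre-existing delirium will in fact be counted: that depends on a positive result at Time 1 which persists, and no Time 1 prevalence is given. The second is that a chance imbalance in such cases would pass for an effect of the exercise. Section 4 says each group is evaluated separately, the outcome is exploratory, no efficacy hypothesis for delirium is stated, and 2/15 against 0/15 gives p = 0.48 even if the Fisher test named in the data analysis plan were applied.

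The consequence is confined to the delirium incidence handed to the next trial. No primary conclusion changes. The change is still worth making before analysis, because it uses data already scheduled and removes a choice between definitions after the results are seen.

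**What to change.** Replace the definition in Section 4 with wording such as:

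*New-onset delirium: negative CAM/4AT at Screening and at Day 1 Time 1, and positive (CAM positive and/or 4AT of at least 4) at one or more of 24, 48 and 72 hours. The denominator is participants negative at both earlier assessments.*

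Then add:

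- For the control arm, the post-operative assessment that serves as Time 1 and the time zero from which 24, 48 and 72 hours are counted.
- Participants positive at Time 1, reported separately by arm.
- The any-positive proportion among all participants, kept as a descriptive line so that every case remains visible.

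The Section 2 endpoint cell and the results table should use the same definition.

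**Cost:** a few sentences in Section 4, a note to the Schedule of Activities for controls, and a revised table layout. The CAM/4AT assessments are already in the schedule. The small downside is that the new-onset denominator may lose a few participants per arm.
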